Protocol Title:

Patient- and Task-specific Radiation Dose Optimization for Pediatric Abdominopelvic CT Applications

NCT03429712

Purpose of the Study:

To implement a recently validated single-energy dual-source multi-detector computed tomography (DSSE) dose split technique in a cohort of pediatric patients to determine, without increase in patient radiation dose, the optimal patient-specific and task-specific radiation dose levels for pediatric abdominal CT applications.

Our working hypothesis is that by using a DSSE dose split technique, we will be able to compare reader diagnostic accuracy for detection of disease across a broad range of different radiation dose levels, without the need of multiple CT acquisitions or artificial noise insertion tools.

We postulate that our research will have important clinical implications. By generating datasets at different (including sub-mSv) radiation dose levels from a single DSSE acquisition within the same patient, the dose split technique will minimize the impact of important confounding variables for the assessment of dose reduction strategies, including inter-patient or inter-scan variability. This will enable more accurate and precise optimization of CT radiation dose according to patient size, diagnostic task, and reconstruction algorithm. It will also accelerate the development and validation of novel reconstruction or noise reduction algorithms, facilitating determination of minimally acceptable dose levels for a wide range of diagnostic tasks.

Background & Significance:

Radiation dose reduction has been a primary driver of technology development and research in multi-detector computed tomography (MDCT). The basic tradeoff of dose reduction is that a reduction in the radiation exposure is unavoidably associated with a reduction of image quality. The most common example of image quality degradation is the increase in image noise ('mottle') in the CT images which can compromise diagnosis. By decreasing the statistical noise associated with low photon count projection data (low dose), iterative reconstruction (IR) methods offer the potential for substantial radiation dose reductions, while providing diagnostic-quality images. Although previous studies have indicated the potential for a radiation dose reduction of up to 75% using IR methods for routine abdominal applications, there is significant variability in the literature regarding the specific recommendations for dose reduction. This observation highlights the critical need to precisely and accurately determine to what degree the radiation dose can be decreased using IR methods without compromising diagnostic image quality. This unmet need is a significant barrier to the effective clinical implementation of IR methods.

Although many factors may have contributed to this large inter-study heterogeneity — including technical differences among rapidly evolving IR methods and important differences in study design and clinical tasks — we postulate that the lack of data from large clinical trials has been one of the primary sources of variability. Previous studies from both phantom and clinical studies have shown a substantial discrepancy in the recommended minimum dose level required to maintain adequate diagnostic performance. This observation may be partially explained by the limitations of traditional surrogate markers of image quality (such as noise magnitude and contrast-to-noise ratio), which cannot capture the nonlinear changes in noise (i.e., noise texture) and image quality using IR methods. This is further compounded by the inherent difficulty in translating data from phantom experiments to the complex human system.

Newer generation dual-source MDCT platforms enable the reconstruction of image datasets at different radiation dose levels from a single CT acquisition. Recent studies have shown that, when both radiation tubes are operated at the same tube potential and tube current (i.e., dual-source single-energy [DSSE] acquisition mode), half-dose and full-dose images can be reconstructed from the same CT acquisition using the projection data of only one tube or both tubes, respectively. Of note, because each x-ray tube in a dual-source CT system has its own generator, it is technically possible to set up individual adjustments of the output (and thus radiation dose) of each radiation tube during a DSSE acquisition. The separate reconstruction of the projection data of each tube independently or the combination of both tubes expands the number of different radiation exposure datasets that can be reconstructed from a single DSSE acquisition within the same patient, thus providing a powerful methodology for assessing the potential radiation dose reduction using IRs.

This strategy overcomes some of the major limitations of previous studies comparing different radiation exposure levels from separate study cohorts (an approach that is confounded by potentially large inter-patient variability) or the utilization of artificial noise insertion tools to simulate reduced-dose CT datasets. Furthermore, compared to multiple single-energy CT acquisitions at different radiation dose levels, a variable dose split DSSE protocol eliminates the need for multiple intravenous contrast material injections and avoids potential variability due to misregistration among different datasets secondary to patient motion or differences in contrast material timing.

Design & Procedures:

This is a prospective Health Insurance Portability and Accountability Act-compliant study for which we are asking for Authorization from the Institutional Review Board.

A non-inferiority statistical analysis was performed for comparing the reconstruction algorithms SAFIRE-3 at 50% and 37.5% radiation exposure against the reference FBP at 100% using the readers' score of overall image

quality as the primary outcome measure. The reader-to-reader and patient-to-patient variability were estimated from actual data [1]. The power analysis results – shown in Figure 1 – demonstrate that with 4 readers a power of more than 80% to test for non-inferiority is achieved with approximately 50 patients. We will select 100 total consecutive pediatric patients undergoing clinically-indicated MDCT of the abdomen and/or pelvis as part of their clinical care. One half (N = 50) of patients will have an indication of *acute* abdominal/pelvic pain/abnormality and the other one half (N = 50) will have an *oncologic* abnormality with indication for imaging of the abdomen and pelvis. Patients will be considered ineligible if they have any contraindication to iodinated contrast material, such as a previous history of anaphylactoid reaction or renal failure (serum creatinine level > 2.0 mg/dL [177 µmol/L]). Women of childbearing potential or refusing urine pregnancy *test* or with a positive test result will be also excluded.

All MDCT examinations will be performed using a second-generation or third-generation dual-source MDCT platform (Somatom Definition FLASH or Somatom Definition FORCE, Siemens Healthcare, Forchheim, Germany), which are equipped with a research-only acquisition mode DSSE dose split software. This software allows the system to be operated in DSSE mode and the effective tube current time product to be adjusted by the user for each tube independently. Each patient will be scanned using a DSSE dose split technique before or after intravenous contrast medium administration during the arterial and/or venous phases matching the medical indication. Patient radiation dose exposure as well as image quality will be comparable to a standard of care MDCT examination, as indicated in our recently published research indicating the experience in 21 patients [1]. The tube output (CTDI_{vol}) for each DSSE acquisition will be selected to match the typical tube output of a conventional MDCT acquisition for a specific CT protocol and patient size. Examples of typical tube output parameters for DSSE acquisitions in pediatric patients are provided below and are based on Duke standard of care protocols for pediatric patients:

		kVp	Pitch	Effective mAs	mAs / rotation	Relative CTDI _{vol} (%)	Relative DLP (%)
Pediatric abdomen and pelvis	Tubes 1 + 2	120	1.2	200	200	100	100
	Tube 1	120	1.2		160	80	80
	Tube 2	120	1.2		40	20	20

State of the art radiation protection features will remain in place, like automatic exposure control of the tube current, which adapts the x-ray tube current according to the patient body habitus relative to a quality reference value. In pediatric examinations additional bowtie filters will be utilized.

By using the project CT data of each x-ray tube independently (A or B) or in combination (A+B), we will reconstruct multiple radiation dose levels for the same patient and same phase of contrast enhancement, ranging from 20% up to 100% dose. The 100% dose dataset will be sent to PACS routinely without delay and used for routine clinical interpretation of the CT examinations.

Images will be reconstructed at 5.0 and 0.6 mm slice thickness using a conventional FBP and two commercially available IR methods: sinogram-affirmed iterative reconstruction (SAFIRE) and advanced modeled iterative reconstruction algorithm (ADMIRE). The SAFIRE and ADMIRE algorithms allow the user to select a strength parameter between one and five that controls how aggressively the algorithm reduces noise. Images will be reconstructed using different strengths, including a strength of three (the recommended setting for abdominal imaging applications according to the manufacturer), four, and five.

In addition, we will collect relevant clinical and demographic patient's information, such as indication for the exam, medical record number, age, gender, and body weight, height, and body mass index. We will also collect information regarding the CT parameters, radiation dose, and image quality. The latter assessment will be performed based on both qualitative (by means of readers and model observer studies) and quantitative metrics of image quality (such as contrast, noise, contrast-to-noise ratio, and spatial resolution).

All raw and reconstructed CT datasets will be stored on a dedicated and password-protected server in the Department of Radiology. The image reconstruction process will take place within the radiology department on a radiology owned and maintained workstation.

Selection of Subjects:

Fifty patients with acute abdominal/pelvic pain/abnormality and fifty patients with an oncologic abnormality undergoing clinically-indicated MDCT of the abdomen and/or pelvis as part of their clinical care will be eligible for inclusion in the study.

Subject Recruitment and Compensation:

Consent Process:

Subjects will be selected through a prospective review of the CT schedule for the Radiology Department. Prior approval from the subject's physician will be obtained prior to enrollment into the study, and the study will be introduced to the potential subject by a caregiver familiar to them per the Policy Statement Regarding Recruitment 10/22/2007.

The study coordinator will consent the eligible participant or legal guardian in the case of a minor according to the inclusion criteria provided in the Design & Procedure section. If necessary, the participants will have no less than 24 hours to consider their participation. Consenting will take place in a private room. The prospective participant may have family or a friend present during the consent process, if they wish. At least an hour will be slotted for the consent process, but we will not prevent the subject from asking questions beyond that time. If the subject wishes to consider the study overnight or longer, an additional appointment will be made for the subject to continue the consent process. From

the time of initial contact until the participant completes the study they will have complete freedom to access the coordinator by phone, email, or in person.

There will be no financial compensation for participation to this study.

Subject's Capacity to Give Legally Effective Consent:

Subjects without capacity to give consent will not be recruited in this study.

Study Interventions:

All patients will undergo a clinically-indicated MDCT examination using a DSSE dose split technique. Patient radiation dose exposure as well as image quality will be comparable to a standard of care MDCT examination.

Risk/Benefit Assessment:

The only identifiable risk for this study is the unlikely but not impossible loss of confidentiality. We have taken all the precaution to minimize this risk. Identifiable PHI will remain with their respective CT exam on a radiology department server and on PACS. HIPAA trained Duke personnel will have access to these exams, and only HIPAA trained Duke personnel will be involved in the study. For each exam, a date, exam protocol type, patient name, and patient ID number will be recorded. Files containing these ID numbers and the dates of the exams will be kept by one of the investigators on a password-protected computer.

Costs to the Subject:

There will be no cost to the patients entered in the study.

Data Analysis & Statistical Considerations:

The two patient cohorts (those with acute abdominal/pelvic pain/abnormality and oncologic process) will be evaluated in concert utilizing the following methodology.

To ensure consistency and reproducibility of the data, measurements of noise and image quality will be performed on a dedicated secondary workstation unit (Core2 x6800; Intel, Santa Clara, Ca) equipped with a previously validated custom Matlab-based software (Matlab, Ver. 2009a, Math-Works, Natick, Ma). Patient anterior abdominal subcutaneous fat will be used for noise assessments and different abdominal organs and vascular structures will be used. To ensure consistency and reproducibility of the data, all measurements will be repeated ten times on three consecutive images along the z-axis.

Four separate image quality figures of merit (FOM) will be measured from the images of each subject. These FOMs will include the contrast-to-noise ratio (CNR), the Rose model signal-to-noise ratio (SNR), the nonprewhitening matched filter detectability index ($d'NPW$), and the nonprewhitening matched filter with eye filter detectability index ($d'NPWe$). Each of these metrics will be analyzed using a repeated measures linear model where the repeat

measurements are across the different dose levels and different reconstruction algorithms. The predictors in linear model will be (a) the radiation dose (b) reconstruction algorithms. We will also examine if there is an interaction between dose and reconstruction algorithm. The estimated effects from the linear model will be used to identify the optimal dose and reconstruction combination.

Also, the noise power spectrum (NPS) and task-transfer function (TTF) will be reported for each reconstruction algorithm. The NPS and TTF are both components of the d' FOM.

Observer data analysis will be performed. Subjective image quality will be assessed in a blinded and randomized fashion by at least 4 independent radiologists. To minimize the effect of recall bias from the interpretation of multiple data sets within the same patient, data sets will be presented to readers over multiple sessions separated by a 2-4 week interval. All patient identifiers will be removed from images. Readers will rank image quality on a 100-point scale. Image quality attributes will be evaluated, including the following: 1) sharpness (defined as the discreteness of the margin of liver and splanchnic vasculature); 2) noise (defined as the amount of graininess or mottle of the image); 3) artifacts (including beam hardening or streaks due to metal or high-density materials such as residual barium within the colonic lumen); and 4) overall image quality (regarded as the reader's desire to use a certain image appearance to confidently detect the presence or absence of intraabdominal or intrapelvic abnormality). Standardized criteria will be presented to readers in a training session just prior to image evaluation session. Readers will be asked to detect the abnormality(s) within the abdomen or pelvis and rate their confidence in detection on a 100-point scale. With interpretation of multiple studies reconstructed at multiple dose intervals over a defined time interval, reader fatigue will also be assessed on the basis of lesion detection ability and/or subjective assessment of self-reported reader fatigue.

Data & Safety Monitoring:

Each CT dataset included in our study will have patient data associated with it on PACS and on the radiology department server. From each dataset, the necessary image reconstructions will be made on a workstation within the radiology department by a Duke radiologist. Qualitative scoring of the reconstructed images will take place in the radiology department by Duke radiologists. For each exam, a date, exam protocol type, patient name, and patient ID number will be recorded. PHI will be kept on a password-protected computer and will be deleted from the data after publication, thus leaving no link to identifiable PHI.

Privacy, Data Storage & Confidentiality:

Every effort will be made to ensure subjects' confidentiality. All images containing subject PHI will remain on PACS and on the radiology department server. PHI recorded with data will be kept in a file on a password-protected

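### The aim is patient- and task-specific dose levels, but the only specified model has no body-size term and states no result by indication

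*Combined protocol and SAP*

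**What the plan says.** - **Aim.** The Protocol Title is "Patient- and Task-specific Radiation Dose Optimization for Pediatric Abdominopelvic CT Applications", and the Purpose of the Study is to determine "the optimal patient-specific and task-specific radiation dose levels for pediatric abdominal CT applications". The same section expects the technique to enable "optimization of CT radiation dose according to patient size, diagnostic task, and reconstruction algorithm", and mentions "facilitating determination of minimally acceptable dose levels for a wide range of diagnostic tasks" as a further benefit.
- **Model.** Data Analysis & Statistical Considerations specifies a repeated measures linear model for CNR, Rose SNR, d'NPW and d'NPWe, each analysed separately. "The predictors in linear model will be (a) the radiation dose (b) reconstruction algorithms"; their interaction will also be examined. The estimates are then used to identify the best pairing of dose and reconstruction, worded in the singular.
- **Cohorts.** Fifty children with an acute indication and fifty with an oncologic one are to be evaluated *in concert* by that method. No comparison between them is stated.
- **Size.** Design & Procedures says that tube output is "selected to match the typical tube output of a conventional MDCT acquisition for a specific CT protocol and patient size" and that exposure control adapts tube current to body habitus. It collects indication and "age, gender, and body weight, height, and body mass index", but no analysis uses them.
- **Readers.** The power statement concerns readers' overall image quality: "with 4 readers a power of more than 80% to test for non-inferiority is achieved with approximately 50 patients". The observer section describes ratings without giving a model.

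**The concern.** Of the three axes on which the Purpose expects optimization (patient size, diagnostic task, reconstruction algorithm), only the algorithm enters the specified model. A model in dose and algorithm estimates an average over the children fitted. It cannot say whether a small child and a large one, or an acute and an oncologic patient fitted together, reach a given image quality at the same relative dose.

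The repeated-measures structure does not supply this. It allows for correlation within a child, but it neither reports how the metric level changes with size nor lets the dose effect vary with size. Results by size or indication could be produced later from the collected data, but the answer to the title question would then be post hoc.

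**Working it through.** **1. The plan's own figure.** The power above 80% with about 50 patients cannot be reproduced: the available text gives no margin, alpha or variances, and the power figure is not shown. Nothing below depends on it.

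**2. What the model yields under each reading of *in concert*.**

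| Reading | By body size | By indication |
|---|---|---|
| All 100 children pooled | none | none |
| Same method applied to each cohort | none | separate estimates, no stated comparison |

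The body-size column is empty either way, because the predictors are the same two.

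**3. Effect of pooling.** With complete data and 50 + 50 children, a pooled dose contrast is the mean of the two cohort contrasts. It misstates each by half their difference. The documents give no evidence on that difference.

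**4. Why level matters as well as dose effect.** Assume, for illustration only, that d' is proportional to √dose × exp(−b × size), with size in SD units and dose relative to each child's own 100%. On the log scale this has no dose-by-size interaction. If a child of average size reaches some target d' at 50% dose, a child s SD from average needs 0.5 × exp(2bs):

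| b | 1 SD smaller | 1 SD larger |
|---|---|---|
| 0 | 50% | 50% |
| 0.1 | 41% | 61% |
| 0.2 | 34% | 75% |
| 0.3 | 27% | 91% |

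The dose needed changes with size although the dose effect does not. With b = 0 one value is adequate; the planned model cannot tell these cases apart.

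**5. Why the scale must be stated.** Assume a metric proportional to √dose, with full-dose levels of 10 in one cohort and 5 in the other. At 20% dose both lose 1 − √0.2 = 55.3%, that is 5.53 and 2.76 units. The raw scale shows an interaction of 2.76; the log scale shows none.

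**6. What the design can resolve.** With complete data, inference reduces to one dose contrast per child. Its SD is set to 1 because the documents give none. The 95% half-widths are:
- pooled: t(99)/√100 = 0.198
- one cohort: t(49)/√50 = 0.284
- difference between cohorts: t(98) × √(2/50) = 0.397
- change per SD of size: t(98)/√100 = 0.198

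Standard errors relative to pooled, if size is unrelated to cohort:
- one cohort: √2 = 1.41
- at z SD of size, averaged over cohorts: √(1 + z²) = 1.41 at z = 1, and 1.63 at the 10th or 90th centile (z = 1.28)
- one cohort at 1 SD of size: √(2 + 1) = 1.73

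At two-sided 0.05 (assumed), 80% power needs a cohort difference of 0.566 SD or a size slope of 0.283 SD per SD.

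**7. Model size.** Take the three example doses (20, 80, 100%) and seven reconstructions (FBP, SAFIRE 3–5, ADMIRE 3–5). The planned model has 3 × 7 = 21 coefficients. Cohort and size, each with a main effect (1), dose interactions (2) and algorithm interactions (6), add 2 × 9 = 18, giving 39. Adding every three-way term gives 3 × 21 = 63. If every child has every reconstruction, there are 100 × 21 = 2,100 records per metric and slice thickness.

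**The case against.** Several stronger readings are tempting, and the documents do not support them.

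- **That the plan picks one dose for every child.** The four metrics are modelled separately, so there may be one optimum per metric, and one per cohort if the cohorts are fitted separately. Tube output and exposure control also adapt to the child, so a single percentage of that reference already implies different absolute doses. This stands, but it does not show that the same percentage gives the same image quality at every size. The analysis section says only that radiation dose is a predictor, without saying whether it is relative or absolute.
- **That the cohorts are certainly pooled.** *In concert* can mean the same method applied to each cohort, and two cohorts of 50 with a power statement at about 50 patients fit that reading. The estimates by indication would then exist. This leaves body size untouched.
- **That no task-specific result is possible.** The d' indices are task-based, several organs and vessels are measured, and readers perform a detection task. But no task or organ factor is stated, and the documents do not say whether the cohorts are the tasks. This is an ambiguity, not a demonstrated omission.
- **That the reader non-inferiority comparison is undermined.** The criticised model covers the objective metrics only, whereas the power statement takes the reader score as primary. The point does not reach that comparison, beyond the absence of a stated breakdown by cohort.

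It is also fair that patient size appears in the Purpose only as an expected benefit and that *patient-specific* is not defined. Even so, some patient-specific result is the stated purpose, and the model produces none.

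**Conclusion.** The point holds, and should be fixed. For body size the conclusion is firm: no reading of the plan gives a result by size for the objective metrics. For indication it is moderate: the result is absent if the cohorts are pooled, and only the comparison is unstated if they are not. For task, the documents are unclear.

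The averages the model would produce remain valid as averages; they do not answer the patient-specific question. How far they would mislead cannot be established, because the documents give no SDs or effect sizes. The illustrations in the working rest on assumed relationships, and the precision figures on complete data and relative SDs.

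**What to change.** In the model in Data Analysis & Statistical Considerations:

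1. Add cohort (acute or oncologic) and one pre-named continuous size measure already collected, for example weight, as main effects and as interactions with dose and with algorithm. Keep higher-order terms exploratory.
2. State the analysis scale, for example log.
3. Report the estimated metric level with confidence intervals for each dose and algorithm combination, by cohort and at low, median and high body size.
4. State whether *in concert* means pooled or parallel, and whether the cohorts are the tasks.
5. Report the reader overall-quality comparison by cohort as well as pooled.

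**Cost.** Only analysis wording changes; scanning, enrolment and data collection do not. Intervals widen to about 1.41 times pooled for a cohort or at 1 SD of size, and 1.73 times for both together. Interaction tests have limited power, so conclusions should rest on estimates and intervals rather than interaction p-values.

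### The only rule for choosing the optimal dose has no reference, acceptability criterion or lead metric, and the reader comparison used to size the study is not carried into it

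*Combined protocol and SAP*

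**What the plan says.** All references are to the combined protocol and SAP.

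- **Purpose of the Study.** The hypothesis is that "we will be able to compare reader diagnostic accuracy for detection of disease across a broad range of different radiation dose levels", and the benefit claimed includes "facilitating determination of minimally acceptable dose levels for a wide range of diagnostic tasks".
- **Design & Procedures, sizing.** The power analysis concerns non-inferiority, "comparing the reconstruction algorithms SAFIRE-3 at 50% and 37.5% radiation exposure against the reference FBP at 100" percent, with the readers' score of overall image "quality as the primary outcome measure". It reports that "with 4 readers a power of more than 80% to test for non-inferiority is achieved with approximately 50 patients". The planned total is 100 patients, 50 acute and 50 oncologic.
- **Design & Procedures, dose levels.** Reduced-dose images come from tube A, tube B or both together. The example table splits output 80% and 20%.
- **Data Analysis & Statistical Considerations, metrics.** CNR, Rose SNR, d'NPW and d'NPWe are each given a repeated-measures linear model with dose and reconstruction algorithm as predictors, and their interaction is to be examined. Then comes the selection rule: "The estimated effects from the linear model will be used to identify the optimal dose and reconstruction combination".
- **Data Analysis & Statistical Considerations, readers.** At least four radiologists score image quality and detection confidence on 100-point scales. The section announces an observer analysis but gives no model or contrast, and no route from the reader scores to the dose conclusion.

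**The concern.** The study is meant to find how low the dose can go. That requires a reference condition, a statement of how much loss is acceptable, and one outcome on which to judge it. The sizing paragraph supplies a reference and an outcome for the reader scores. The selection rule uses neither and rests on four metrics of equal standing, with no way to settle disagreement among them.

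At stake is the headline conclusion. Two analysts following the text with the same data could report different optimal doses, each with a criterion chosen after seeing the results. Neither conclusion would have to rest on the reader comparison that justified the sample size.

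**Working it through.** **1. The plan's own figure.** The stated power is more than 80% with 4 readers and about 50 patients. It cannot be reproduced: the readable text gives no margin, alpha or variance components, and Figure 1 is not shown. It can only be back-solved, using a paired normal approximation with true difference 0 and reader variance ignored:

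margin / SD of paired difference = (z(1−alpha) + z(0.80)) / √50

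- One-sided alpha 0.025: (1.960 + 0.842) / 7.071 = 0.396
- One-sided alpha 0.05: (1.645 + 0.842) / 7.071 = 0.352

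The claim is therefore attainable but not checkable. The point below does not depend on it.

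**2. The two sections side by side.**

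| Element | Sizing text (Design & Procedures) | Selection rule (Data Analysis) |
|---|---|---|
| Outcome | Readers' overall image quality | Four physical metrics, none leading |
| Reference | FBP at 100% | None stated |
| Conditions | SAFIRE-3 at 50% and 37.5% | All dose and reconstruction combinations |
| Criterion | Non-inferiority (margin may be in Figure 1) | None stated |

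**3. What estimated effects alone deliver.** Assume that, for a fixed reconstruction, a metric is proportional to dose^k. For any k above 0 the largest value is at 100% dose. With k = 0.5 (noise proportional to 1/√dose), the fractions of the full-dose value are √0.80 = 0.894, √0.50 = 0.707, √0.375 = 0.612 and √0.20 = 0.447. Nothing in these numbers marks one dose as the lowest acceptable.

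**4. What a criterion adds.** Let f be the fractional noise reduction from iterative reconstruction (assumed). CNR relative to FBP at 100% is then √dose / (1 − f). The table gives the lowest dose that meets threshold T, taken from the levels named in the documents (20, 37.5, 50, 80, 100%).

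| f | T = 1.00 | T = 0.90 | T = 0.80 | T = 0.70 |
|---|---|---|---|---|
| 0 | 100% | 100% | 80% | 50% |
| 0.2 | 80% | 80% | 50% | 37.5% |
| 0.3 | 50% | 50% | 37.5% | 37.5% |

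For example, with f = 0.3, 50% dose gives 0.707 / 0.7 = 1.010 and 37.5% gives 0.612 / 0.7 = 0.875. If only the example split's levels (20, 80, 100%) exist, f = 0.2 and f = 0.3 both give 80% at all four thresholds. The selection thus depends on the threshold, the noise reduction and the dose grid. All values of f, k and T are assumptions, not estimates for SAFIRE or ADMIRE.

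**5. Whether the powered levels have data.** One acquisition yields shares s, 100 − s and 100. A 50% level needs 50/50, and a 37.5% level needs 37.5/62.5. Since 50 + 37.5 = 87.5, not 100, no single split yields both. The example split yields 20, 80 and 100, so neither. If different patients supplied the two levels in equal numbers, each would have 100 / 2 = 50 patients across both cohorts, or 25 per cohort if evenly spread.

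**6. Power of a two-step sequence.** If each test alone has 80% power, the chance of passing both is at least 0.80 + 0.80 − 1 = 0.60, is 0.80 × 0.80 = 0.64 if the tests are independent, and is at most 0.80.

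**The case against.** The strongest reply is that the rule should be read in context. The Purpose speaks of the lowest acceptable dose and Design & Procedures names FBP at 100% as the reference, so optimal need not mean the largest metric value. This stands in part. A reader might infer that the plan will select 100% dose. The text does not say that the largest effect wins, and 100% is only one literal reading. What remains is that the rule needs a criterion and states none.

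The metric plan is also better than a bare reading suggests. The dose-by-algorithm interaction is to be examined, and it bears directly on whether a reconstruction helps more at low dose. The Background criticises "traditional surrogate markers of image quality (such as noise magnitude and contrast-to-noise ratio), which cannot capture the nonlinear changes in noise", and a reader might infer that this discredits the whole metric set. It does not: d'NPW and d'NPWe incorporate the noise power spectrum and the task-transfer function, which partly answers the criticism. But neither is made the lead metric.

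Three other stronger readings are not supported:

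- **That the non-inferiority margin is missing.** It may be in Figure 1, which is not shown.
- **That the selected dose swings by a known amount.** A continuous curve with k = 0.5 and thresholds of 0.90 and 0.60 gives 0.90² = 81% and 0.60² = 36%, which are 45 points apart. That figure comes from the assumptions, and with f = 0.3 in the table above the move is only 12.5 points.
- **That the powered comparisons cannot be made.** The split table is labelled as examples and each tube is adjustable, so splits may differ between patients. A level with fewer than 100 patients is not in itself underpowered, because the power claim rests on about 50.

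**Conclusion.** The point holds. The plan has one rule for its main conclusion, and that rule lacks a reference, an acceptability criterion and a lead metric. The reader comparison named as primary and used for sizing is not connected to it. This is a textual finding and needs no numerical assumption. That the largest effect falls at 100% does assume that the metrics rise with dose for a fixed reconstruction. No size in percentage points can be attached, because every such figure depends on an assumed threshold, noise reduction and dose grid.

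The dose-level mismatch is a separate matter of arithmetic: no single split gives both powered levels, and the example split gives neither. The sections must be reconciled.

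This should be fixed, but it does not undermine the planned collection of reader scores and metrics. The remedy is mainly analysis wording, plus a clear account of which patients supply which dose level.

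**What to change.** 1. **Primary dose conclusion.** Define it as the lowest pre-listed dose at which SAFIRE-3 is non-inferior to FBP at 100% on readers' overall image quality, using the margin from the sponsor's own power analysis. Test in fixed sequence from higher to lower dose and stop at the first failure. Use a mixed model with patient and reader random effects.
2. **Metric models.** Keep them, with the interaction term, as the supportive analysis for comparing dose and reconstruction combinations, including ADMIRE and the other strengths. State one lead metric, FBP at 100% as reference, and the acceptability criterion before analysis.
3. **Dose levels.** Reconcile the levels in the power analysis, the example table and the reconstruction description so that the powered comparisons have data. State how many patients supply each level, against the approximately 50 on which the power rests.

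**Cost.** The first two items are wording plus a standard multi-reader model on data already planned. The metric models and the other algorithms become supportive rather than confirmatory. Passing both steps of the sequence has a probability of 60% to 80% if each test alone has 80% power. The third item may show that a level rests on fewer patients than the total suggests.
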